	
Or
 
3) ECG manifestations of acute myocardial ischemia (in absence of left ventricular hypertrophy and left bundle branch block) including evolving ST elevation, ST depression, T-wave changes, new pathological Q-waves (R waves in V1-2) in at least two consecutive leads or new left bundle branch block.
 
A complete definition of the criteria for MI can be found in the 2017 Cardiovascular and Stroke Endpoint Definitions for Clinical Trials⁵¹. Peri-procedural infarctions are defined as greater than 3x ULN for serum CK-MB for PCI and greater than 5x ULN for CABG.
	
including intracoronary imaging or by autopsy*
 
cTn indicates cardiac troponin; ECG, electrocardiogram; URL, upper reference limit.
 
*Postmortem demonstration of an atherothrombus in the artery supplying the infarcted myocardium, or a macroscopically large circumscribed area of necrosis with or without intramyocardial hemorrhage, meets the type 1 MI criteria regardless of cTn values.
 
A complete definition of the criteria for MI can be found in the Fourth Universal Definition⁵¹ of Myocardial Infarction (2018). The exception will be for peri-procedural myocardial infarctions, which are defined as biomarker elevation ≥ 10 times the upper reference limit (URL) for creatine kinase MB (CKMB) and/or ≥ 70 URL for troponin as outlined in the most recent SCAI (Society for Cardiovascular Angiography and Interventions) definition⁶⁰.

Table of Abbreviations	Not applicable	CAC: Coronary Artery Calcium added
Table of Abbreviations	Not applicable	SCAI: Society for Cardiovascular Angiography and Interventions
Exclusion criteria	Not applicable	
New exclusion criteria #11 added:
 
11. Known CAD by coronary calcium presence, either by prior CAC scoring or definite coronary calcium reported on a non-cardiac chest CT scan.

Secondary Effectiveness Endpoints	Proportion of invasive cardiac catheterization patients who undergo revascularization (PCI or CABG) within 6 months of enrollment	
“Invasive cardiac catheterization” has been updated to invasive coronary angiogram.
 
Proportion of invasive coronary angiogram patients who undergo revascularization (PCI or CABG) within 6 months of enrollment

V.D. Participa- nt Follow- Up	For North American participants, follow-up after 45 days will be done by phone interviews conducted by the DCRI Outcomes Call Center.	Visit 45 day has been added along with further clarification on site participation: For North American participants, follow-up at 45 days and at 6, 12, and 24 months visits will be done by phone interviews conducted by the DCRI Outcomes Call Center, unless not allowed by their enrolling site.
IV.A Overview of PRECISE- Diagram	 
Diagram from version 1.3.
	
Randomization stratified by preferred first test if usual care and PROMISE risk score.
 
Diagram updated to provide clarification on the pre-randomization step.

Referral of precisio n evaluati on cCTA participants for FFR _{CT} determinatio ns	Image sets showing at least one 30-90% stenosis in epicardial vessels of 2mm diameter or greater will be....	
Language updated to “should” from “will”:
 
Image sets showing at least one 30-90% stenosis in epicardial vessels of 2mm diameter or greater should be

IV.G. Diagnostic Evaluations and Subsequent Care	For patients in the Precision Evaluation Arm, ICA cannot be performed unless at least one of the following criteria are met:	
With this amendment, the language has been softened from “cannot” to “should not”:
 
For patients in the Precision Evaluation Arm, ICA should not be performed unless at least one of the following criteria are met:

IV.E. Rationale for Selection of Testing in Each Arm	Use of cCTA as the initial diagnostic strategy is specifically excluded in the usual care strategy arm and prohibited as a subsequent test for the first 45 days after randomization	
With this amendment, “or a calcium score” has been added to the protocol.
 
Use of cCTA or a calcium score as the initial diagnostic strategy is specifically excluded in the usual care strategy arm and prohibited as a subsequent test for the first 45 days after randomization

IV.E. Rationale for Selection of Testing in Each Arm	The intervention in PRECISE will triage patients into two risk groups who will be assigned to receive either guideline-recommended medical management without planned testing or cCTA with selective FFR _{CT}	"Including no CAC" language has been added with this amendment: The intervention in PRECISE will triage patients into two risk groups who will be assigned to receive either guideline- recommended medical management without planned testing (including no CAC) or cCTA with selective FFR _{CT}
V.C Participant Cohort Assignment	Performance of cCTA as the initial test is excluded in this arm and prohibited as a subsequent test for the first 45 days after randomization.	With this amendment, "or a calcium score" has been added to the protocol. Performance of cCTA or a calcium score as the initial test is excluded in this arm and prohibited as a subsequent test for the first 45 days after randomization.
V.C Participant Cohort Assignment	Participants will be assigned to either guideline-recommended medical management without planned testing (low risk) or cCTA with selective FFR _{CT} (elevated risk).	"Including no CAC score" has been added: Participants will be assigned to either guideline-recommended medical management without planned testing (low risk) including no CAC score or cCTA with selective FFR _{CT} (elevated risk).
References- 51 and 60	Reference 51 51. Hicks KA, Mahaffey KW, et al.	Reference 51 is updated and reference 60 is added with the new amendment v1.4: 51. Thygesen K, Alpert JS, et al 60. Moussa ID, Klein LW, et al

Amendment from version 1.4 dated February 1, 2019 to version 1.5 dated October 15, 2019

Section	Version 1.4	Version 1.5
Investigator Protocol Signature Page	NA	Included separate line for PI signature
Table of Abbreviations	NA	AG: Agatston units
Table of Abbreviations	DECISION: D ecisive E valuation of C ardiac I shemia, S ymptoms and R evascularization	Removed
Table of Abbreviations	HU: Hounsfield units	Removed

IV. Study Overview and Objectives - Study duration	
The anticipated total duration of the PRECISE study will be approximately 48 months for start-up, enrollment, follow up, and close out. Participants will be followed for 24 months after enrollment.
	
Overall study duration reduced to 36 month and patient follow up to 12 month after enrollment.
 
"The anticipated total duration of the PRECISE study will be approximately 36 months for start-up, enrollment, follow up, and close out. Participants will be followed for 12 months after enrollment."

IV.A. Overview of PRECISE – figure of the trial design		 
Figure updated to remove 24 month and co-primary endpoints of DECISION. Arrows leading to GRMT or cCTA annotated "low risk" and "elevated risk" respectively. Patients with known nonobstructive coronary plaque or extensive coronary calcium randomized to the precision arm are mandated to undergo cCTA +/- FFR_{CT}, independent from PROMISE risk score strata.

IV.B. Primary Objective and Endpoints	
Per the exclusion criteria, any previous noninvasive or invasive CV diagnostic testing for suspected CAD must have been >1 year prior to enrollment. Patients with known obstructive CAD (prior myocardial infarction, CABG or PCI, any stenosis $\geq 50\%$) are ineligible for PRECISE.
	
Replaced with:
 
"Patients with known nonobstructive coronary plaque or extensive coronary calcium randomized to the precision arm are mandated to undergo cCTA +/- FFR_{CT}, independent from their PROMISE risk score strata."

IV.C. Secondary Endpoints	
Endpoints will be assessed at 45 days, 6 months, 1 year and 2 years.
	
Removed secondary endpoint assessment at 2 years:
 
"Endpoints will be assessed at 45 days, 6 months and 1 year."

IV.C. Secondary Endpoints	
9. PRECISE primary endpoint at 24 month
	
Removed PRECISE primary endpoint at 24 month

10.	Planned Table of Contents for Analysis Tables and Figures.....	24
11.	Changes from the Protocol	27
12.	References	28
Appendix I.	Schedule of Activities.....	30

[figure not shown]
1. Study Title

Prospective Randomized Trial of the Optimal Evaluation of Cardiac Symptoms and Revascularization (PRECISE).

2. Study Design

The study is a prospective, pragmatic, randomized clinical trial of the comparative effectiveness of diagnostic evaluation strategies for suspected stable CAD, performed in outpatient settings. Qualifying patients are those presenting with new symptoms suspicious for clinically significant CAD (and without known obstructive CAD), who are recommended for diagnostic testing and have not received any testing for cardiovascular ischemia with the past 12 months. Patients meeting these criteria will be randomized to an initial strategy of either precision care or usual care. The Usual Care Arm requires initial testing in all participants using either noninvasive testing (of the site's choice, including stress nuclear, stress echocardiography, stress MRI, or exercise ECG) or invasive testing (invasive coronary angiography) according to the pre-randomization intended testing strata. cCTA and calcium scoring are prohibited as a subsequent test for the first 45 days after randomization. Participants randomized to the Precision Evaluation Arm will be assigned to either no immediately planned testing, if Low Risk (see derivation below), or cCTA with selective FFR_{CT} if Elevated Risk or with known non obstructive atherosclerosis. If Low Risk participants develop a need for testing, such increasing angina, cCTA with selective FFR_{CT} must be used. All subsequent decisions in the usual care arm regarding additional testing, medications, and/or procedures are at the discretion of the responsible clinical care team.

See Figure 1 for a description of the participant flow.

Figure 1. Participant flow in the study.

3. Objectives

The primary objective of the PRECISE trial is to compare the clinical outcomes, downstream decision making regarding noninvasive testing and invasive angiography, and costs of using a precision care with a usual care strategy in participants with stable symptoms suggestive of coronary artery disease. The precision care will start with a pre-test risk assessment. Participants at low risk will be managed initially without cardiac diagnostic testing. Participants not at low risk and those with known atherosclerosis will undergo cCTA with selective FFR_{CT} as the initial evaluation. These results will inform the decision to use invasive coronary angiography. All participants in the trial will also receive guideline-recommended care with symptom and risk factor management.

This SAP contains definitions of analysis populations, derived variables, and details on the statistical methods for the analyses and summaries of study data for the PRECISE trial. This SAP will supersede the protocol in defining the trial endpoints and analysis plans. Mock ups of tables, figures, and data listings are contained in a separate document. A draft list of planned tables and

figures to be created from the final trial data sets can be found in section 10 of this document. Some of these tables and figures will be created as part of the Clinical Study Report and will not be duplicated in the Statistical Report. Details of the economic endpoints analyses are presented in a separate PRECISE Economics and QoL SAP.

4. Analysis Endpoints

4.1 Primary Endpoint

The PRECISE primary endpoint will be a composite of three participant outcomes and will be measured (in days) as the time to first occurrence during a 12 month (365 days \pm 30 days) trial follow-up of: 1) all-cause death, 2) non-fatal myocardial infarction, (MI) or 3) invasive cardiac catheterization without obstructive CAD (obstructive CAD defined as diameter stenosis $\geq 50\%$ according to core-lab adjudicated quantitative coronary angiography or site read in an epicardial vessel >2 mm, or FFR ≤ 0.80 or iFR ≤ 0.89). (See section 9.2 for more detail along with figure describing derivation of the cath catheterization component of the primary endpoint).

4.1.1 Secondary Endpoints

The following secondary endpoints will be assessed using Benjamini-Hochberg procedure (Benjamini and Hochberg, 1995).

1. Hierarchical analysis of the primary endpoint using the unmatched win ratio method
2. Resource use patterns and medical costs (See PRECISE Economics and QoL SAPs)
3. QoL measured by the Seattle Angina Questionnaire (SAQ) summary score to assess angina-specific QoL, and the EuroQoL 5D (EQ-5D-5L) survey to assess overall (generic) health status (See PRECISE Economics and QoL SAPs)

4.1.2 Additional Protocol Specified Endpoints

Additional protocol-defined endpoints include:

1. Death, including separate analyses for all-cause and cardiovascular
2. Nonfatal MI, including separate analyses for all, procedural, and spontaneous
3. Hospitalizations, including separate analyses for all-cause, cardiovascular and for progressive or unstable angina.
4. Preventive medication use, defined as use of aspirin/anti-platelet drugs and/or statins, in participants with clinical indication for use
5. Cumulative trial strategy-related radiation exposure
6. Proportion of participants who undergo revascularization (PCI or CABG) within 6 months of diagnostic catheterization, overall, and controlling for rates of diagnostic catheterization.

4.2 Pre-specified Subgroup Analyses

4.2.1 Primary endpoint subgroup analyses

The following subgroup treatment/strategy comparisons will be conducted for the primary endpoint at 12 months as a forest plot with an interaction p-value.

1. Demographic and clinical subgroups

- Sex: Male/Female
- Age: <65, 65 to 74, \geq 75 years
- Race/ethnicity:
 - White/non-Hispanic vs. other
- Risk score:
 - Low vs. elevated (All Participants);
 - Low vs. elevated (excluding known obstructive atherosclerosis);
 - Above and below PRECISE median score

Risk score cut point based on the top 10% of low risk of the PROMISE Risk Score in the PROMISE cohort. Low Risk is defined as an absolute score >0.46 (see derivation in section 6.1 below).
- History of diabetes: Yes/No
- History of CAD/PAD/abnormal ABI: Yes/No
- Obesity: (BMI< 25, 25-30, >30)
- Geographic region: United States vs. Outside the United States

2. Intended first test is noninvasive vs. invasive
3. Symptoms and risk subgroups at presentation/randomization
 - Primary symptom presentation: 1) Typical Angina, 2) Atypical Pain, 3) Dyspnea, and 4) Non-Cardiac Pain/other
 - ESC modified Diamond-Forrester Pre Test Probability score (2019) with the population divided as <5% pretest probability, 5-15%, and $>15\%$.
 - Tertiles of ASCVD risk score
 - SAQ angina score at presentation: More frequent angina ($</= 80$) vs. Rare/absent angina (>80)

5. Population Treatment Assignment for Analysis

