A sensitivity analysis for the primary composite MACE (all cause death and non-fatal MI) or invasive cardiac catheterization without CAD (no coronary stenosis $\geq 50\%$ according to QCA by core-lab adjudication or site interpretation if QCA is not available, or with $FFR \leq 0.80$, or instantaneous wave free ratio (iFR) ≤ 0.89) endpoint will be conducted using the method of “win-ratio”⁵⁶ and Finkelstein and Schoenfeld rank-test method⁵⁷. More details on primary, secondary and sensitivity analyses will be provided in the complete Statistical Analysis Plan (SAP).

Subgroup analyses

Subgroup analyses will be performed to assess whether the intervention effect is consistent across all participants, or whether it varies according to specific participant characteristics. In particular, these analyses will focus on whether the relative intervention effect compared to usual care differs according to the following baseline variables:

- Low risk vs. elevated risk by PROMISE Risk score or presence of known non-obstructive atherosclerosis
- Intended first test: functional vs. invasive
- Sex (male vs. female)
- Age (<65, 65 to 74, and >75 years)
- History of diabetes
- Presentation: primary symptom (chest pain vs. other), SAQ angina score (daily/weekly angina at baseline versus less frequent)
- Geographic region (US, Canada, Europe, Other Regions)

These analyses will utilize the Cox model and will be accomplished by testing for interactions between the randomized treatment strategy and the specific baseline variables listed above. In addition to the formal assessment of treatment by covariate interactions, the effect of the treatment strategy characterized by a hazard ratio and 95% confidence interval will be calculated and displayed using a forest plot for the subgroups of participants defined by the variables listed above. These descriptive hazard ratios will be carefully interpreted in conjunction with the formal interaction tests.

The effect of the treatment strategy may also be examined in other subgroups of clinical interest in addition to those listed above.

Analysis of the Secondary Endpoints

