Sample size and power calculations for this study are based on the hypothesis that the precision evaluation arm is superior to the usual care arm on the time-to-first event of the composite 3-component endpoint: all-cause death, non-fatal MI, or invasive cardiac catheterization without obstructive CAD (obstructive CAD defined as diameter stenosis $\geq 50\%$, FFR ≤ 0.80 , or iFR ≤ 0.89) over a 12-month of follow-up. Time to event analysis will use the date of the event, including the date of catheterization at which the absence of obstructive CAD is demonstrated. Assuming 10% of usual care participants will receive angiography as a first test results in an 8% primary endpoint event rate at 1 year in the usual care group and 5% event rate in the precision care group (i.e., 3% absolute [37.5% relative] effect size). Assumptions used in the primary endpoint event rate calculations (i.e., 8% vs. 5%) were: overall 10% will not receive randomized evaluation, and within the precision evaluation arm, approximately 20% will be assigned to guideline-recommended care with symptom management and no planned testing, of whom about 30% will have escalation of care to cCTA with selective FFRCT.

Randomizing 1050 participants per group (2100 total participants) is estimated to provide at least 90% power to detect a relative risk reduction of 37.5% in the precision evaluation arm (see Table 1 below, or refer to the power curves in the protocol). Sample size/power calculations are based on the log-rank test with 12-month accrual period, a minimum 12-month follow-up (i.e. last participant will be followed for at least 12-months), 10% attrition rate (i.e. lost to follow-up, dropouts) and a two-sided type I error rate of 0.05.

The DSMB will review interim analysis data for efficacy as well as possible sample size re-estimation. At any interim analyses, the O'Brien-Fleming boundary generated by Lan-DeMets alpha-spending function will be utilized as a statistical stopping rule (See DSMB charter for more details).

Table 1. The total number of participants needed for 85%, 90%, and 95% power. Although this is not an event-driven study, the table below also provides total number of MACE needed.

1-year event rate in precision evaluation arm	Power	Total number of Primary Events needed	Total number of participants needed
(37.5% ^{2%} effect size)	85%	173	1792
	90%	202	2096
	95%	250	2592

8. Database Sources

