9.1 General Approach

Continuous variables will be summarized as means (standard deviations), medians (25th and 75th percentiles), minimum and maximum. Number (percentage) of participants in each category will be presented for categorical variables. Comparisons of categorical variables between the two randomized arms or between pre-specified subgroups will be performed using Pearson's chi-square test or Fisher's exact test depending on expected cell sizes; comparisons of continuous variables will be performed using the Wilcoxon rank-sum test.

Unless otherwise stated, all hypothesis tests will be performed using two-sided tests. No adjustment for multiplicity is planned.

All primary statistical analyses will be conducted using the intention-to-treat principle to define treatment assignment, except as indicated.

In addition to the pre-specified subgroup analyses (see Section 9.4), response magnitude analyses may be considered, in which participants are evaluated based on a binary variable indicating improvement or no improvement with respect to a given assessment.

[figure not shown]
Analyses will be performed using SAS software version 9.4 or higher (SAS Institute, Inc., Cary, NC).

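### Interaction p-values for the PROMISE score (PRECISE-median split) and the ASCVD score (tertiles) rest on data-driven cuts, and no continuous interaction is planned: a cheap improvement

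*SAP*

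**What the plan says.** SAP section 4.2.1 introduces its list with "The following subgroup treatment/strategy comparisons will be conducted for the primary endpoint at 12 months as a forest plot with an interaction p-value". Under the PROMISE risk score it has the low/elevated contrast at 0.46 (in all participants and with an exclusion) and a further item, "Above and below PRECISE median score". Among the presentation variables it has "Tertiles of ASCVD risk score". Age, BMI and pre-test probability each appear in three bands, and the SAQ angina score is cut at 80.

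SAP section 9.4 refers back to this list for judging whether the effect is consistent across participants. The model is named in the protocol (VIII.B, Subgroup analyses): a Cox model, "testing for interactions between the randomized treatment strategy and the specific baseline variables listed above". SAP section 9.1 adds "No adjustment for multiplicity is planned".

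Neither document plans an interaction with a modifier kept continuous. Age enters the adjusted Cox model of SAP 9.2 only as a covariate. SAP 9.3.4.1 assesses the prognostic calibration and discrimination of the PROMISE score, not effect modification. The SAP does not say whether three-level factors are tested on 2 df or as a 1-df trend.

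**The concern.** The trial tests a risk-based strategy, so whether its effect varies with baseline risk is close to the scientific question. A median or tertile cut treats everyone within a group as having the same risk. If the effect changes gradually with risk, the information within groups is lost to the interaction test.

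These two cuts are also the hardest to defend as the source of a p-value. They depend on who happens to enrol, match no stated clinical threshold, and would fall elsewhere in another population. Interaction power is limited to begin with because few primary events are expected. A further loss makes it more likely that a real gradient in effect goes undetected.

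**Working it through.** **The plan's own figure.** SAP section 7 assumes a design that "results in an 8% primary endpoint event rate at 1 year in the usual care group", a "5% event rate in the precision care group", and "10% attrition rate (i.e. lost to follow-up, dropouts) and a two-sided type I error rate of 0.05". The implied HR is ln(0.95)/ln(0.92) = 0.615. Schoenfeld events for 90% power are 4 × (1.960 + 1.282)² / (ln 0.615)² = 178.04, rounded up to 179. With 12-month accrual and at least 12 months of follow-up, the mean event probability is 0.0956. So N = 179/0.0956/0.9 = 2080, against 2096 in Table 1; 179/0.9 = 199 events, against 202. The main-effect calculation reproduces. The documents give no interaction power and no target interaction size.

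**Events.** At 12 months, 1050 × 0.08 + 1050 × 0.05 = 136.5. With censoring at 395 days (SAP 9.2) and 10% attrition taken as 0.9N, the count is 2100 × 0.9 × 0.0701 = 132.6.

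**Assumptions.** 1:1 allocation (SAP section 6); two-sided 5% for each interaction test (none is stated); normal modifier; log-HR changing by b per SD. I use b = 0.2 to 0.5, that is, a ratio of hazard ratios of 1.22 to 1.65 per SD.

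**Information kept** is the between-group share of the modifier's variance.
- Median split: 2/π = 0.637, so 36% is lost.
- Tertiles: outer group means are ±0.3636/(1/3) = ±1.091, giving (2/3) × 1.091² = 0.793, so 21% is lost.

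**Power.** The noncentrality is (events/4) × b² × information kept, referred to a noncentral chi-square. For b = 0.3 and 136.5 events it is 34.125 × 0.09 = 3.07 (continuous), × 0.637 = 1.96 (median) and × 0.793 = 2.44 (tertiles).

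| b per SD | Continuous | Median split | Tertiles, 2 df | Tertile trend, 1 df |
|---|---|---|---|---|
| 0.2 | 21.5% | 15.4% (−6.1) | 14.0% (−7.5) | 18.0% (−3.5) |
| 0.3 | 41.8% | 28.8% (−13.0) | 26.7% (−15.1) | 34.5% (−7.3) |
| 0.4 | 64.7% | 46.2% (−18.5) | 44.5% (−20.1) | 54.8% (−9.9) |
| 0.5 | 83.2% | 64.5% (−18.7) | 64.0% (−19.2) | 73.9% (−9.2) |

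Over all effect sizes the formula's largest loss for the 1-df trend is 10.0 points.

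**Sensitivity to the event count.** With 202 events the losses (median split; 2-df tertiles) are 9.0 and 10.8 points at b = 0.2, 17.0 and 18.9 at 0.3, 19.0 and 19.7 at 0.4, and 13.5 and 12.8 at 0.5. The picture does not turn on the event count.

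**Simulation check.** Cox likelihood-ratio tests with 2100 participants, about 136 events and a ratio of hazard ratios of 1.62 per SD gave 77.9% (continuous), 56.2% (median), 56.4% (2-df tertiles) and 67.4% (trend). These gaps of 21.7, 21.5 and 10.5 points are slightly larger than the formula's.

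**The case against.** **A step, not a slope.** In the precision arm the assigned evaluation changes at a PROMISE score of 0.46, and known atherosclerosis overrides the score, so a linear log-HR may be the wrong shape. The score is also a bounded probability, not a normal variable. This stands as a limit. For a normal modifier with a step exactly at the median, the linear term keeps only 2/π = 64% of the information, so the 36% loss runs the other way. But the known threshold is not the PRECISE median. Taking about 20% as low risk (SAP section 7), a step there leaves the linear term 0.280²/(0.2 × 0.8) = 49% of the information under normality. The median split keeps (0.2 − 0.2 × 0.5)²/(0.16 × 0.25) = 25%. A step at the care threshold therefore does not rescue the median cut.

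**Other modifiers.** A reader might infer that age, BMI, SAQ and pre-test probability lose the same 21 to 36%. The documents do not support that, because they give no group shares. Under normality an assumed 20/80 cut would lose 51%, so 36% is not even an upper bound. Nor are all these bands arbitrary: 15% pre-test probability appears in the guideline discussion in protocol IV.E, and the SAQ cut is labelled as separating more frequent from rare or absent angina.

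**Size of the interaction.** The 13-to-20-point range depends on interactions of 0.3 to 0.5 per SD, which are large beside a planned overall log-HR of ln(0.615) = −0.49. This stands, which is why the smaller loss at 0.2 belongs in the conclusion.

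**Are the scores numeric?** The SAP gives no ASCVD derivation, but forming tertiles already requires an ordered score. The PROMISE formula in SAP 6.1 returns a number even when HDL is missing.

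**Consequence.** These analyses are supportive, and the protocol says subgroup hazard ratios will be read together with the interaction tests. Nothing equates a non-significant test with proven consistency.

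**Conclusion.** The point holds for two items, the PRECISE-median split of the PROMISE score and the ASCVD tertiles. For a roughly normal modifier with a linear log-HR interaction, these cuts discard about 36% and 21% of the information. With about 137 events the cost is about 6 to 8 power points at 0.2 per SD and 13 to 20 points at 0.3 to 0.5 per SD; a 1-df tertile trend would lose at most about 10. The distributions and the interaction sizes are assumptions, since the documents give neither. A true step at a cut would remove or reverse the gain.

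A reader might go further and infer that the trial's main conclusion is weakened, or that a continuous test would make a null interaction result reliable. Neither follows. The primary log-rank test does not use these groupings, and continuous-test power is itself only 22%, 42% and 65% at 0.2, 0.3 and 0.4 per SD. This is a cheap improvement to supportive analyses, not a defect in the primary analysis.

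**What to change.** In SAP 4.2.1 and 9.4:

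- Take the interaction p-value for the PROMISE score and the ASCVD score from a Cox model with arm by continuous value, using a linear term with a 3-knot spline as a check.
- Keep the listed categories for the forest-plot hazard ratios.
- Keep the low/elevated (0.46) binary interaction test, and the clinically defined pre-test probability and SAQ bands, as planned.
- For age, BMI, SAQ and pre-test probability, add the continuous interaction as a supplementary test only.
- State whether the remaining three-level factors are tested on 2 df or as a 1-df trend.

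The cost is SAP wording and a few extra model fits, with no new data. There are two downsides: the linear term is an assumption, which the spline checks only in part, and for the two scores the forest-plot rows and the p-value will use different codings of the same variable, which a footnote should say. The change should be fixed before outcome data by arm are seen. SAP 9.4 already allows further subgroups chosen after initial analyses, so a continuous model added later would look data-driven.
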